5.1.3 Subject Exclusion Criteria

The subject must be excluded from participating in the trial if the subject:

1. Has primary ocular melanoma.
2. Is currently participating and receiving study therapy or has participated in a study of an investigational agent and received study therapy or used an investigational device within 4 weeks of the first dose of treatment.
3. Has received systemic immunosuppressive steroid therapy or any other form of systemic immunosuppressive therapy for treatment of prior immune-related adverse events or other indications within 7 days prior to the first dose of trial treatment. Exception: Physiologic corticosteroid replacement therapy for adrenal or pituitary insufficiency is not considered systemic immunosuppressive steroid therapy.
4. Has received previous high dose ($\geq 600,000$ IU/kg) IL-2 therapy. Any other prior therapy (in the adjuvant or the metastatic setting) is allowed, including immunotherapy, targeted therapy, chemotherapy, and experimental therapy.
5. Has a history of significant congestive heart failure or significant pulmonary disease
6. Has a known history of active TB (Bacillus Tuberculosis)
7. Hypersensitivity to pembrolizumab or any of its excipients, or a known history of hypersensitivity to IL-2 or any component of the formulation.

████████████████████
████████████████████

8. Has had a prior anti-cancer monoclonal antibody (mAb) within 4 weeks prior to study Day 1 or who has not recovered (i.e., \leq Grade 1 or at baseline) from adverse events due to agents administered more than 4 weeks earlier.
9. Has had prior chemotherapy, targeted small molecule therapy, or radiation therapy within 2 weeks prior to study Day 1 or who has not recovered (i.e., \leq Grade 1 or at baseline) from adverse events due to a previously administered agent.
 - Note: Subjects with \leq Grade 2 neuropathy and/or alopecia are exceptions to this criterion and may qualify for the study.
 - Note: If subject received major surgery, they must have recovered adequately from the toxicity and/or complications from the intervention prior to starting therapy.
10. Has a known additional malignancy that is progressing or requires active treatment. Exceptions include basal cell carcinoma of the skin or squamous cell carcinoma of the skin that has undergone potentially curative therapy or in situ cervical cancer.
11. Has known active central nervous system (CNS) metastases and/or carcinomatous meningitis. Subjects with previously treated brain metastases may participate provided they are stable (without evidence of progression by imaging for at least four weeks prior to the first dose of trial treatment and any neurologic symptoms have returned to baseline), have no evidence of new or enlarging brain metastases, and are not using steroids for at least 7 days prior to trial treatment. This exception does not include carcinomatous meningitis which is excluded regardless of clinical stability.
12. Has a history of inflammatory bowel disease.
13. Has past medical history of autoimmune disease (e.g. Crohn's disease, Rheumatoid arthritis, etc.) that has required systemic treatment in the past 2 years (i.e. with use of disease modifying agents, corticosteroids or immunosuppressive drugs).
14. Has a history of (non-infectious) pneumonitis that required steroids or current pneumonitis..
15. Has an active infection requiring systemic therapy.
16. Has a history or current evidence of any condition, therapy, or laboratory abnormality that might confound the results of the trial, interfere with the subject's participation for the full duration of the trial, or is not in the best interest of the subject to participate, in the opinion of the treating investigator.
17. Has known psychiatric or substance abuse disorders that would [REDACTED] the requirements of the trial.

- 18. Is pregnant or breastfeeding, or expecting to conceive or father children within the projected duration of the trial, starting with the pre-screening or screening visit through 120 days after the last dose of trial treatment.
- 19. Has a known history of Human Immunodeficiency Virus (HIV) (HIV 1/2 antibodies).
- 20. Has known active Hepatitis B (e.g., HBsAg reactive) or Hepatitis C (e.g., HCV RNA [qualitative] is detected).
- 21. Has received a live vaccine within 30 days of planned start of study therapy.

Note: Seasonal influenza vaccines for injection are generally inactivated flu vaccines and are allowed; however intranasal influenza vaccines (e.g., Flu-Mist®) are live attenuated vaccines, and are not allowed.

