5.1.2 Subject Inclusion Criteria

In order to be eligible for participation in this trial, the subject must:

1. Histologic or cytologic diagnosis of cutaneous melanoma, mucosal melanoma, or melanoma of unknown primary that is considered unresectable (Stage III) or metastatic (Stage IV).
2. Be willing and able to provide written informed consent/assent for the trial.
3. Be ≥ 15 years of age on day of signing informed consent.
4. Have measurable disease evident on radiographs (preferred) or clinical examination. For this protocol, measurable disease is defined as at least one evaluable tumor that is at least 10 mm in longest dimension.
5. Have a performance status of 0 or 1 on the ECOG Performance Scale (See Appendix 11.1 for classification criteria).
6. Patients must have a brain MRI or CT (with and without contrast) that is free of active metastases. Metastases that have been treated with radiation or surgical resection, are stable for at least 4 weeks and do not require steroids are eligible.
7. Normal cardiac function. Patients who have a history of heart disease, or who are over the age of 50 years must have a normal cardiac stress test within the prior 90 days.

8. Normal lung function. Patients who have extensive pulmonary metastases or any chronic pulmonary disease history must have pulmonary function testing demonstrating FEV1 and FVC > 65% of predicted values.
9. Demonstrate adequate organ function as defined in Table 1,

Table 1. Adequate Organ Function Laboratory Values

System	Laboratory Value
Hematological	
Absolute neutrophil count (ANC)	≥1,500 /mcl
Platelets	≥100,000 / mcl
Hemoglobin	≥9 g/dL or ≥5.6 mmol/L without transfusion or EPO dependency (within 7 days of assessment)
Renal	
Serum creatinine OR Measured or calculated* creatinine clearance (GFR can also be used in place of creatinine or CrCl)	≤1.5 X upper limit of normal (ULN) OR ≥60 mL/min for subject with creatinine levels > 1.5 X institutional ULN
Hepatic	
Serum total bilirubin	≤ 1.5 X ULN OR Direct bilirubin ≤ ULN for subjects with total bilirubin levels > 1.5 ULN. Patients with Gilbert's Syndrome must have a total bilirubin < 3.0 mg/dL.
AST (SGOT) and ALT (SGPT)	≤ 2.5 X ULN OR ≤ 5 X ULN for subjects with liver metastases
Albumin	>2.5 mg/dL
Coagulation	
International Normalized Ratio (INR) or Prothrombin Time (PT)	≤1.5 X ULN unless subject is receiving anticoagulant therapy as long as PT or PTT is within therapeutic range of intended use of anticoagulants

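### Entry rules test only present recovery, so a patient can enroll after a resolved PD-1/PD-L1 immune event of a type and grade that would permanently stop pembrolizumab on study

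*SAP*

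**What the plan says.** Three exclusion criteria in SAP Section 5.1.3 deal with earlier immunotherapy and its toxicity.

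- Criterion 4 bars earlier high-dose IL-2 and nothing else: "Any other prior therapy (in the adjuvant or the metastatic setting) is allowed, including immunotherapy, targeted therapy, chemotherapy, and experimental therapy".
- Criterion 3 excludes systemic immunosuppression given "for treatment of prior immune-related adverse events or other indications within 7 days prior to the first dose of trial treatment".
- Criterion 8 requires 4 weeks since the last anticancer antibody, and recovery to Grade 1 or baseline "from adverse events due to agents administered more than 4 weeks earlier".

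Other criteria touch on the patient's history.

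- Criterion 14: "Has a history of (non-infectious) pneumonitis that required steroids or current pneumonitis".
- Criterion 12: "Has a history of inflammatory bowel disease".
- Criterion 13: "Has past medical history of autoimmune disease", limited to disease treated systemically in the past 2 years.
- Criterion 5: "Has a history of significant congestive heart failure or significant pulmonary disease".
- Inclusion criterion 7 (Section 5.1.2) asks for normal cardiac function and adds: "Patients who have a history of heart disease, or who are over the age of 50 years must have a normal cardiac stress test".
- Criterion 16 lets the treating investigator exclude a patient whose history makes participation unwise. It sets no threshold.

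Table 3 (Section 5.4.1) sets out when pembrolizumab is withheld and when it is permanently stopped for immune-related events during study treatment. Section 2.1 expects many participants to have had a PD-1 antibody already. Section 4.1.2.1 describes pembrolizumab as a first-line standard option, and no criterion bars earlier use of it.

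**The concern.** Criteria 3, 4 and 8 describe the patient's state at entry: how long since treatment, and what grade of toxicity remains. The worst grade reached on the earlier drug plays no part. On study, the worst grade decides. For several event types Table 3 ends pembrolizumab permanently, and later recovery does not reopen it.

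A patient could therefore be re-exposed to the same drug class, possibly the same drug, after an event that this protocol treats as final when it happens under its own care. Re-exposure comes with IL-2. The combination rationale in Section 4.2 says the two side-effect profiles overlap in part, and Section 4.1.3.2 reports that IL-2 often raises creatinine and bilirubin. Safety is a primary objective (Section 3.1.1), and dose escalation begins with a cohort of 3 (Section 5.3). One severe recurrence would matter to the patient and could also cloud the reading of the combination's tolerability.

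**Working it through.** No formula applies. The check sets each permanent-stop event in Table 3 against every entry criterion in Sections 5.1.2 and 5.1.3. It takes a patient whose event on an earlier anti-PD-1/PD-L1 drug has resolved to Grade 1 or baseline, who has been off immunosuppression for more than 7 days, whose last antibody was more than 4 weeks ago, and who meets the organ-function limits in Table 1.

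| Event that permanently stops pembrolizumab on study (Table 3) | Entry criterion that bears on it once resolved | Result |
|---|---|---|
| Pneumonitis, Grade 3-4 or recurrent Grade 2 | Criterion 14, if steroids were needed | Excluded |
| Myocarditis, Grade 3-4 | Inclusion 7 and criterion 5 | Partly filtered |
| Diarrhea/colitis, Grade 4 | Criterion 12 names inflammatory bowel disease, not drug-induced colitis | No specific bar |
| AST/ALT or bilirubin elevation, Grade 3-4 | Table 1 tests current values only | No specific bar |
| Nephritis or renal dysfunction, Grade 3-4 | Table 1 tests current values only | No specific bar |
| Guillain-Barre syndrome, encephalitis | None | No specific bar |
| Other immune-related events, Grade 4 or recurrent Grade 3 | None | No specific bar |

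Of seven event groups, one is closed, one is narrowed and five are open, apart from investigator discretion under criterion 16.

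Criterion 13 might be thought to close more of the gap, because steroid treatment of an immune-related event within 2 years looks like systemic treatment of autoimmune disease. Two things speak against that reading. Its examples are primary autoimmune diseases. And criterion 3 speaks expressly of immunosuppression for earlier immune-related events and asks for only 7 days off it, which would serve little purpose if criterion 13 already excluded such patients for 2 years.

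Criterion 14 also shows that entry and on-study rules differ in both directions. It excludes any steroid-treated pneumonitis, whereas Table 3 only withholds for a first Grade 2 episode. For lung, entry is the stricter rule; for liver, kidney and nervous system it is the looser one. The visible rationale in Section 4.2 gives no reason for this pattern.

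**Size.** Section 4.1.2.2 reports immune-related events in 21.4% of melanoma patients on pembrolizumab, with rates for some types such as diarrhea (2.2%) and pneumonitis (1.9%). These are not broken down by grade. Hepatic, renal, cardiac and neurological events are not among the listed types. The share of participants with earlier PD-1 treatment is given only as many. A count of affected patients would need the rate of permanent-stop grades by type and the pretreated share, and the documents supply neither.

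**The case against.** The best defense is that this is a choice and not an oversight. Criterion 3 names earlier immune-related events and sets a rule for them, criterion 8 adds a recovery standard, and criterion 14 adds a history bar where the authors wanted one. Nothing in the plan says entry must mirror Table 3. Restarting a drug in the middle of treatment and enrolling a patient after washout and recovery are different decisions. Criterion 16 must be considered for every patient, and a past life-threatening event on the same drug class falls within its scope. Table 1 guards current liver and kidney function, inclusion 13 requires that the patient meet the institution's requirements for IL-2, and Table 3 would act on any recurrence.

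Much of this stands. A reader might infer that the protocol contradicts itself, saying yes at entry and no on study to the same event. The documents do not support that: Table 3 is confined to events associated with pembrolizumab given in the trial and takes no position on earlier ones. A reader might also try to build an upper bound on affected patients from the any-grade rates in Section 4.1.2.2. That bound would rest on assumed rates for event types the section does not list and would count low-grade events that are not at issue, so it would say little.

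What remains is that criterion 16 has no threshold, so two sites may decide differently about the same patient. The visible text also offers no argument for rechallenge after a permanent-stop event.

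**Conclusion.** The point holds as a safety misalignment. Apart from steroid-treated pneumonitis, partial cardiac filters and investigator discretion, the entry rules admit a patient after a resolved immune-related event on an earlier anti-PD-1/PD-L1 drug for which Table 3 would permanently stop pembrolizumab if it arose on study. It is worth correcting because the possible harm is serious, the trial recruits from the population at risk, and the remedy is short. The number affected cannot be computed and is probably small, which limits the priority.

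The conclusion assumes that criteria 12 and 13 do not reach drug-induced events, as their wording suggests. It also assumes that no further eligibility rule stands elsewhere. Sections 6 to 10 and the companion guidance on events of clinical interest were not available for this check, but the exclusion list runs unbroken from 1 to 21. Confidence is medium.

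**What to change.** Add to criterion 8 in Section 5.1.3, and to its copy in the Section 1.0 synopsis, a clause such as:

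> or who, on a prior anti-PD-1 or anti-PD-L1 agent, had an immune-related Grade 3-4 hepatic event, Grade 3-4 nephritis, Grade 3-4 myocarditis, Grade 4 diarrhea/colitis, Guillain-Barre syndrome, encephalitis, or, for event types without their own row in Table 3, a Grade 4 or recurrent Grade 3 immune-related event; endocrinopathy controlled with hormone replacement (or, for type 1 diabetes, with metabolic control) is exempt.

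Limits of the clause:

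- Recurrent Grade 3 colitis stays eligible, because the colitis row of Table 3 only withholds at Grade 3. That is why the last event category is restricted to types without their own row.
- Pneumonitis stays under criterion 14.
- The endocrinopathy exemption follows the resumption note under Table 3.
- Table 3's 12-week non-resolution rule and its open-ended list of Grade 3 events are left out. The first would catch slow-resolving events that are otherwise only withheld for, and the second gives sites no fixed line.
- Table 3 names the two neurological syndromes in its Grade 3 line. The clause takes them at any grade, which is slightly stricter; add a grade if exact parity is wanted.

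The cost is one clause in two places and a few fewer eligible patients. Patients pretreated with PD-1 drugs who had no such event remain eligible, so the trial's purpose is unaffected.

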5.2 Trial Treatments

The treatment to be used in this trial is outlined below in **Table 2**

Table 2 Trial Treatment

Drug	Dose/ Potency	Dose Frequency	Route of Administration
Pembrolizumab	200 mg flat dose	Q3W	IV infusion
	6,000 IU/kg		
IL-2	60,000 IU/kg	Q8H	IV bolus
	600,000 IU/kg		
	600,000 IU/kg		

5.2.1 Pembrolizumab

5.2.1.1 Treatment Setting and Timing

Trial treatment should be administered after all procedures/assessments have been completed as detailed on the Trial Flow Chart (Section 6.0). Trial treatment should be administered on Day 1 of each indicated week, but may be administered up to 7 calendar days before or after the scheduled Day 1 due to administrative reasons (\pm 7 day window).

Pembrolizumab will be given in the outpatient setting during study visits that do not contain IL-2 treatment. When the visit includes hospitalization for IL-2 administration, pembrolizumab may be given in the inpatient setting. On days when both drugs are given, IL-2 administration should commence **1-8 hours after completion of the pembrolizumab infusion**.

5.2.1.2 Dosing

All subjects will be treated with pembrolizumab given at a flat dose of 200 mg IV every 3 weeks per Trial Flow Chart. The flat dose will be used whether given in combination with IL-2 or given as monotherapy.

Pembrolizumab 200 mg will be administered as a 30 minute IV infusion every 3 weeks. Sites should make every effort to target infusion timing to be as close to 30 minutes as possible. However, given the variability of infusion pumps from site to site, a window of -5 minutes and +10 minutes is permitted (i.e., infusion time is 30 minutes: -5 min/+10 min).

The Pharmacy Manual contains specific instructions for the preparation of the pembrolizumab infusion fluid and administration of infusion solution.

5.2.1.3 Pembrolizumab Monotherapy

Subjects who do not tolerate IL-2 will be permanently discontinued from IL-2 and will finish the treatment period on pembrolizumab monotherapy (200 mg IV Q 3 weeks until the end of the treatment period, which is defined as 2 calendar years from the date of enrollment), provided that treatment is not discontinued earlier to due unacceptable toxicity or significant progression of disease. The subject does not need to continue to meet all eligibility criteria to continue to receive treatment.

5.2.1.4 Discontinuation of Pembrolizumab for patients with confirmed CR

Subjects who achieve a complete response (CR) will continue to receive pembrolizumab Q 3 weeks until 1) the CR is confirmed, and 2) they have received treatment for 6 months (defined as 24 ± 3 weeks) from the date of the first instance of unconfirmed CR. If both criteria are met, the subject will have the option to discontinue pembrolizumab treatment. These subjects should have Safety Assessments with clinical and laboratory evaluation Q 6 weeks and tumor assessments will continue to be Q 12 weeks per the trial flow chart (Section 6.0). If the tumor assessments during the remainder of the 2 year study period show reoccurrence of disease while off treatment, the patient may resume treatment on the trial. The maximum active treatment period is 2 years including treatment breaks.

5.2.2 II-2

5.2.2.1 Treatment Setting and Timing

All doses of II-2 will be administered in the inpatient setting. II-2 will be given intravenously (IV) every 8 hours for up to 14 doses in each cycle. The 8 hour dosing is a guideline and doses may be delayed or omitted per investigator discretion and/or institutional guideline (no strict window).

II-2 will be administered according to standard institutional guidelines and in accord with current clinical practice guidelines for II-2 administration [34]. Concomitant medications must be reviewed prior to each cycle of II-2.

Antihypertensive medication: Patients with a history of hypertension who are taking concomitant outpatient antihypertensive medications must discontinue these medications 48H prior to admission. Upon discharge from the hospital to home, patients should resume their antihypertensive medications (other than betablockers) during the week between cycles, usually starting 48 hours after discharge. If patients are planning additional II-2 treatment they should not re-start betablockers. Examples of betablockers include: metoprolol, carvedilol, nebivolol, labetalol, sotalol, propranolol, oxprenolol, pindolol, penbutolol, and acebutolol.

Supportive concomitant medications are necessary during II-2 therapy to decrease toxicity. A prophylactic antibiotic, such as oxacillin, must be administered to prevent catheter-related infections during the hospitalization. Special precautions should be made when using the following medications with II-2: psychotropic drugs, nephrotoxic medications, cardiotoxic medications, and contrast media. Benzodiazepines, sleeping aides, and haloperidol are sometimes indicated as supportive medications. Indomethacin is typically given every 6-8 hours during II-2 treatment to manage fever if the creatinine remains below 3.0 mg/dL, but other nephrotoxic medications should be avoided if possible, especially the use of IV contrast media, which should be avoided for two weeks following II-2 therapy.

Typically, 2 cycles of IL-2 make up a course of IL-2. The duration of a cycle is the duration of hospitalization (approximately 3-7 days). Admission for IL-2 will occur at Weeks 4, 7, 16, 19, 28, and 31 as per the Study Flow Chart in Section 6.0. IL-2 may not be given earlier or later than the allotted window (± 7 days). A minimum rest period of 9 days is required in between admissions to the hospital. If an admission for IL-2 is moved up or delayed, the pembrolizumab will be moved up or delayed as well to be given on the same day as the IL-2.

On days when pembrolizumab and IL-2 are scheduled to be administered together, pembrolizumab should be administered first, followed by IL-2 administration, which should commence 1-8 hours after the completion of pembrolizumab infusion.

The following should be done daily during IL-2 administration: neurologic assessment, complete blood count, blood chemistries, chest x-ray, vital signs, pulse oximetry, weight, and fluid intake and output.

5.2.2.2 Dosing of IL-2 in the Phase Ib Portion

Patients in the Phase Ib portion of the study will be assigned to a dose cohort of IL-2 upon study entry.

Level	Dose of IL-2 (IV bolus Q 8 hrs)	Dose of pembrolizumab
1	6,000 IU/kg	200 mg
2	60,000 IU/kg	200 mg
3	600,000 IU/kg	200 mg

5.2.2.3 Dosing of IL-2 in the Phase II portion

All subjects will be treated with the MTD of IL-2. If no MTD is reached in the Phase Ib portion, the 600,000 IU/kg dose will be called the MTD.

5.2.2.4 Calculation of IL-2 Dose

Calculate Total Dose as follows: $\text{Desired dose of IL-2 in IU/kg} \times \text{Patient body weight in kg} = \text{IL-2 dose in IU}$.

Based on the investigator's discretion, IL-2 dose can be calculated using the actual or ideal body weight.

Calculate Rate of Infusion as follows: $\text{Infusion volume in ml} \div 15 \text{ minutes} = \text{rate of infusion in ml/min}$.

5.2.2.5 Determining Number of Courses of IL-2

Subjects who experience an SAE of Special Interest (see Section 7.2.1.4) during IL-2 therapy or other significant IL-2-related toxicity in the treating physician's opinion should be discontinued from IL-2. Subjects may decline additional IL-2. Subjects in whom IL-2 is discontinued for these reasons should be treated with pembrolizumab monotherapy Q 3 weeks.

Subjects who achieve SD or an unconfirmed/confirmed PR should repeat the course of IL-2 and, at the discretion of the treating investigator, and may receive up to 3 courses of IL-2 in combination with pembrolizumab. For example, subjects who have regressing lesions not meeting RECIST criteria for PR (classified as SD) would be expected to continue IL-2 and pembrolizumab Q 3 weeks, provided that toxicity is acceptable. All protocol treatment (IL-2 and pembrolizumab) should continue until CR is achieved or removal from study. Subjects who achieve an unconfirmed or confirmed CR should be discontinued from IL-2.

